9.15. Pharmacodynamics of Voruciclib and Voruciclib + Venetoclax

Blood will be collected for determination of the effect of voruciclib monotherapy and the combination of voruciclib + venetoclax on biomarkers, e.g., apoptotic pathway proteins, and to correlate antitumor activity with baseline tumor characteristics, according to the following schedules, as follows:

Monotherapy Cohorts 6a,b – 8a,b

- Cycle 1 Day 1: Pre-dose, and approximately 6-hours post-dose
- Cycle 1 Day 2: Pre-dose (approximately 24 hours after preceding dose)
- Cycle 1 Day 15: Pre-dose (approximately 24 hours after preceding dose)

Combination therapy Cohorts 12–19 and 21–25:

- Cycle 1 Day 1: Pre-dose of venetoclax and approximately 6-hours post-dose of venetoclax for Cohorts 12–16 or 4–6 hours post-dose for Cohorts 17–25
- Cycle 1 Day 3: Pre-dose of voruciclib and approximately 6-hours post-dose of voruciclib for Cohorts 12–16 or 4–6 hours post-dose for Cohorts 17–25
- Cycle 1 Day 14*: Pre-dose of venetoclax and approximately 6-hours post-dose of voruciclib for Cohorts 12–16 or 4–6 hours post-dose for Cohorts 17–25

*For Cohort 12, since there is no voruciclib dosing on Cycle 1 Day 14, blood will be collected on Cycle 1 Day 13 pre-dose of venetoclax and approximately 6-hours post-dose of voruciclib during clinic visit for PK sample collection.

For PK and PD collection visits that fall on weekends or holidays, please contact the Sponsor to discuss sampling schedule.

10. STATISTICS

10.1. Number of Subjects

At the start of Amendment 12, a total of 40 subjects have been enrolled in the now-completed monotherapy dose escalation/expansion cohorts. Assuming an average enrollment of 4 subjects per dose level for DLT evaluation, up to 12 subjects to be enrolled in the 2 combination AML expansion cohorts, and an additional 10% for early drop-outs due to non-evaluability after failure to complete Cycle 1 treatment for reasons other than AEs related to voruciclib, the total enrollment for the voruciclib plus venetoclax combination group is estimated to be approximately 68 subjects, for a total of approximately 108 subjects to be enrolled in the study.

10.2. Study Endpoints

The primary study objectives are to determine the safety and tolerability and safe and mBED of voruciclib monotherapy in subjects with relapsed and/or refractory B-cell malignancies and AML and to determine the safety, tolerability and safe and mBED of voruciclib in combination with venetoclax in subjects with relapsed and/or refractory AML.

Safety will be assessed by AEs graded according to NCI CTCAE v5.0; laboratory safety tests including hematology (CBC), serum chemistry; physical examination; vital signs; ECOG performance status; and triplicate 12-lead ECG. If 2 or more of 6 subjects experience a DLT in a dose cohort, then the next lower dose will be the MTD.

The primary endpoint is:

- The incidence of AEs, including DLTs.

Secondary endpoints are:

- Efficacy endpoints within each tumor type:
 - a. Overall Response Rate (ORR), defined as the proportion of subjects who achieve a best overall response of
 - CR, CRi, or PR, with responses defined per 2008 International Workshop on CLL (IWCLL) guidelines,
 - CR or PR by 2014 Lugano criteria for non-Hodgkin lymphoma,
 - CR, CRi, CR_{MRD}, MLFS by the 2017 ELN criteria for AML
 - b. DOR defined as the time from first achieving a response to date of documented disease progression or death from any cause. Subjects who die due to any cause prior to progression will be censored
 - c. PFS defined as time from first dose of study drug to date of documented disease progression or death from any cause
 - d. Estimates of the exposure and association with efficacy and safety variables for voruciclib administered as monotherapy, and the PK of voruciclib and venetoclax when administered in combination

The exploratory endpoints are:

- a. Effects on biomarkers and functional activities of proteins in the apoptotic pathway
- b. Correlations of anti-tumor activity and baseline tumor characteristics

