 - If >1 of 6 subjects have a DLT, this dose level will be declared as not safe, further dose escalation on IS_{2w,2w} will not proceed, and Cohort 9 will be studied.
 - If ≤1 of 6 subjects have a DLT, the study will continue to enroll in Cohort 7.
- Cohort 7: 150 mg QD, administered IS_{2w,2w}
 - If 0 of 3 subjects have a DLT, this dose and schedule will be declared safe for either dose escalation to Cohort 8 or evaluation of 3 additional subjects in Cohort 7; this will be determined by the SRC based on PK and clinical results.
 - If >1 of 3 subjects have a DLT, this dose will be considered as not safe, further dose escalation will not proceed, and 3 subjects will be enrolled in Cohort 6 (for up to 6 evaluable subjects in Cohort 6) to confirm it is the MTD.
 - If 1 of 3 subjects have a DLT, 3 more subjects will be enrolled in Cohort 7.
 - If >1 of 6 subjects have a DLT, this dose level will be considered as not safe for further evaluation and 3 additional subjects will be enrolled in Cohort 6 to confirm it is the MTD. However, if Cohort 6 has previously enrolled 6 subjects with ≤1 DLTs, then the Cohort 6 dose level will be declared the MTD.

- If ≤ 1 of 6 subjects have a DLT, this dose and schedule will be declared safe for either dose escalation to Cohort 8 or evaluation of that dose in an expansion cohort; this will be determined by the SRC based on PK and clinical results.
- Cohort 8: 200 mg QD, administered $IS_{2w,2w}$
 - If 0 of 3 subjects have a DLT, this dose and schedule will be declared safe, and 3 additional subjects will be enrolled in Cohort 8 to confirm it is the MTD.
 - If >1 of 3 subjects have a DLT, this dose will be considered as not safe, and 3 subjects will be enrolled in Cohort 7 (for up to 6 evaluable subjects enrolled in Cohort 7) to confirm it is the MTD.
 - If 1 of 3 subjects have a DLT, 3 more subjects will be enrolled in Cohort 8.
 - If >1 of 6 subjects have a DLT, this dose level will be considered as not safe for further evaluation and 3 additional subjects will be enrolled in Cohort 7 to confirm it is the MTD. However, if Cohort 7 has previously enrolled 6 subjects with ≤ 1 DLTs then Cohort 7 dose level will be declared the MTD.
 - If ≤ 1 of 6 subjects have a DLT, this dose and schedule will be declared safe for cohort expansion.

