Only the tablet formulation containing the voruciclib malonate salt will be used in the voruciclib plus venetoclax combination group.

Table 3: Dose Cohorts with Combination Voruciclib + Venetoclax (Amendment 11)

Cohort Dose Level	Doses and Schedule
12	voruciclib 50 mg QOD, administered IS _{2w,2w} + venetoclax administered QD × 28 days
13	voruciclib 50 mg QD, administered IS _{2w,2w} + venetoclax administered QD × 28 days
14	voruciclib 100 mg QD, administered IS _{2w,2w} + venetoclax administered QD × 28 days
15	voruciclib 150 mg QD, administered IS _{2w,2w} + venetoclax administered QD × 28 days
16	voruciclib 200 mg QD, administered IS _{2w,2w} + venetoclax administered QD × 28 days
17	voruciclib 250 mg QD, administered IS _{2w,2w} + venetoclax administered QD × 28 days
18	voruciclib 300 mg QD, administered IS _{2w,2w} + venetoclax administered QD × 28 days
19	voruciclib 350 mg QD, administered IS _{2w,2w} + venetoclax administered QD × 28 days

Abbreviation: QOD = once every other day

At the completion of the DLT period for each cohort, decisions to escalate in subsequent cohorts will be guided by SRC review of all available safety data, PK and PD data.

For Cohort 12, the dosing of voruciclib will be Days 3, 5, 7, 9, 11, and 13 of Cycle 1, and Days 1, 3, 5, 7, 9, 11, and 13 of Cycle 2 and beyond.

Dose escalation to the next cohort will be initiated after 3 subjects have completed 1 cycle with no reported DLTs, or after 6 subjects have completed 1 cycle with no more than 1 DLT (as defined in [Section 4.4](#)) and with the approval of the SRC after review of safety from the cohort under review.

Intra-patient dose escalation to the next dose in Cycle 2 or later cycle is allowed at the discretion of the investigator and after consultation with the Sponsor if the next dose level has been declared safe by the SRC. More specifically, a subject enrolled at a dose level X may have their dose escalated to the next dose level X + 1 after completing Cycle 1 without a DLT.

Dose escalation proceeds until assessment of clinical and PK parameters by the SRC establishes the safe BED for voruciclib in combination with venetoclax. More specifically, a voruciclib dose in combination with venetoclax that meets the following criteria:

- DLT not to exceed 1 in 6 patients, overall response rate (ORR) $\geq 30\%$, as compared to historical ORR of 19% with 400-800 mg venetoclax alone in relapsed/refractory AML ([Konopleva 2016](#)), and

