4.6. Maximum Tolerated Dose (MTD)

With respect to voruciclib monotherapy, for each disease group and schedule (continuous, IS_{2w,2w}, IS_{1w,3w}), an MTD of voruciclib will be defined as the highest dose at which <2 of 6 subjects experience a DLT.

With respect to voruciclib +venetoclax combination therapy, an MTD will be defined as the highest dose cohort level at which <2 of 6 subjects experience a DLT.

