## 4. SAMPLE SIZE DETERMINATION

The MTD will be determined employing a standard 3 + 3 design. For voruciclib monotherapy, because enrollment will be conducted independently in subjects with AML and B-cell malignancies, within each disease group, dose and regimen changes will follow the 3 + 3 design, summarized below. Initially, 3 subjects will be enrolled at the lowest dose level in IS2w,2w in each disease group:

- If 0 of 3 subjects experience a DLT during Cycle 1, another 3 subjects will be enrolled at the next higher dose level.
- If > 1 of 3 subjects have a DLT during Cycle 1, this dose level will be declared as not safe, further dose escalation on the IS2w,2w regimen will not proceed, and IS1w,3w evaluating a less intensive dose regimen will be studied.
- If 1 of 3 subjects experiences a DLT during Cycle 1, an additional 3 subjects will be enrolled at the same dose level, with dose escalation permitted only if there are no additional DLTs.
- If > 1 of 3 subjects experience a DLT (in all but the lowest dose level) during Cycle 1, the next lower dose level within the IS will enroll an additional 3 subjects (for a total of 6 subjects).
  - If ≤ 1 of 6 subjects experience a DLT during Cycle 1, this dose level will be declared the MTD.
  - If > 1 of 6 subjects experience a DLT (in all but the lowest dose level) during Cycle 1, the next lower dose level within the IS will enroll an additional 3 subjects.\*

\*Within each disease group in a dose cohort, if the next lower dose regimen had previously enrolled 6 subjects, then the lower dose regimen will be declared the MTD.

For voruciclib + venetoclax combination therapy in AML, the same standard 3 + 3 design will be followed for voruciclib dose escalation on the IS2w,2w regimen.

At the start of Amendment 11, a total of 33 subjects have been enrolled in Cohorts 1, 2, 6a, 6b, 7a, 7b and 8a; the AML monotherapy expansion cohort enrolled 6 subjects. Assuming an average enrollment of 4 subjects per dose cohort for DLT evaluation, up to 12 subjects to be enrolled in the combination AML expansion cohort, and an additional 20% for early drop-outs due to non-evaluability after failure to complete Cycle 1 treatment for reasons other than AEs related to voruciclib, the total enrollment for initial dose/regimen escalation phase is estimated to be approximately 100 subjects for monotherapy (AML and B-cell malignancies), combination therapy (AML) and expansion cohorts.

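### Read literally, Protocol 10.2 makes the next lower dose the MTD even if only 3 subjects were treated there, contradicting Protocol 4.6, Protocol 4.3.1.2 and SAP 4

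*Protocol*

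**What the plan says.** **The sentence at issue.** In the paragraph on safety assessment, Protocol 10.2 states: "If 2 or more of 6 subjects experience a DLT in a dose cohort, then the next lower dose will be the MTD". No condition is placed on the number treated, or the DLTs seen, at that next lower dose.

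**The definition.** Protocol 4.6 says for monotherapy that "an MTD of voruciclib will be defined as the highest dose at which <2 of 6 subjects experience a DLT", and for the combination that "an MTD will be defined as the highest dose cohort level at which <2 of 6 subjects experience a DLT". Both use a denominator of 6.

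**Escalation.** A dose can be passed on 3 subjects. Protocol 4.3.2 says "Dose escalation to the next cohort will be initiated after 3 subjects have completed 1 cycle with no reported DLTs", or after 6 subjects with at most 1 DLT.

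**Back-fill for monotherapy.** When more than 1 of 6 subjects at Cohort 7 have a DLT, Protocol 4.3.1.2 says "3 additional subjects will be enrolled in Cohort 6 to confirm it is the MTD". Its exception is narrow: "However, if Cohort 6 has previously enrolled 6 subjects with ≤1 DLTs, then the Cohort 6 dose level will be declared the MTD".

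**Back-fill in the SAP.** After more than 1 DLT in 3 above the lowest dose, SAP 4 says "the next lower dose level within the IS will enroll an additional 3 subjects (for a total of 6 subjects". It repeats the 3-subject addition after more than 1 DLT in 6. The exception is that "if the next lower dose regimen had previously enrolled 6 subjects, then the lower dose regimen will be declared the MTD". For the combination, SAP 4 adopts the same 3+3 design and names the IS2w,2w schedule only.

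**IS3w,1w.** The protocol synopsis and Protocol 4.3.2 say these cohorts follow the 3+3 design of the IS2w,2w cohorts and share their definitions of DLT, MTD and mBED.

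**The concern.** The same trigger, 2 or more DLTs among 6 subjects, leads to two different actions. Under Protocol 10.2 the dose below becomes the MTD at once. Under Protocol 4.3.1.2 and SAP 4 the dose below is first brought to 6 subjects, unless it already has them. A committee following 10.2 could name an MTD on 3 evaluable subjects, half the number that the 4.6 definition uses.

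Monotherapy is complete (Protocol 10.1), so the conflict now matters for the combination cohorts, where the text is thinnest. Protocol 4.3.2 gives the condition for going up but writes out no step for going back down and filling the lower dose. Protocol 4.6 supplies the definition but not the action that follows 2 DLTs. The situation can readily arise: Protocol 4.3.2 reports no DLTs on IS2w,2w from 50 mg QOD to 250 mg QD, so the 3-subject route was open at each of those levels. The documents do not give the number treated at each level.

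At stake is how often a dose that is too toxic is called the MTD, and how little is known about the DLT rate at the dose so named.

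**Working it through.** **Inputs.** Passing routes are 0/3, or 1/3 then 0/3 (Protocol 4.3.2). The MTD criterion is at most 1 DLT in 6 (Protocol 4.6). The true DLT rate p is not given, so 20% to 50% is assumed. The lower end is the range of about 20 to 25% that Protocol 10.3 says the 3+3 design targets at the MTD.

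**The plan's own figure.** That 20 to 25% depends on a dose-toxicity curve that the documents do not give, so it cannot be strictly reproduced. Simulating the 3+3 on four assumed curves (40,000 runs each) gave a mean true DLT rate at the declared MTD of about 18 to 22%, broadly in line with it.

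**Formulas.**
- A, passed on 0/3: (1−p)³
- B, overturned by 3 more subjects (2 or more DLTs): 3p²(1−p) + p³
- C, 0/3 then at most 1 DLT in 3 more: A × (1−B)
- D, any passing route: A + 3p(1−p)²(1−p)³
- E, at most 1 DLT in 6 required: D − A × B

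Example at p = 0.30: A = 0.7³ = 0.343; B = 3 × 0.09 × 0.7 + 0.027 = 0.216; C = 0.343 × 0.784 = 0.269.

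| p | A | B | C | D | E | A/D |
|---|---|---|---|---|---|---|
| 0.20 | 0.512 | 0.104 | 0.459 | 0.709 | 0.655 | 72% |
| 0.25 | 0.422 | 0.156 | 0.356 | 0.600 | 0.534 | 70% |
| 0.30 | 0.343 | 0.216 | 0.269 | 0.494 | 0.420 | 69% |
| 0.40 | 0.216 | 0.352 | 0.140 | 0.309 | 0.233 | 70% |
| 0.50 | 0.125 | 0.500 | 0.063 | 0.172 | 0.109 | 73% |

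B is the share of 0/3 doses that the missing step would catch. A/D shows that about 70% of passed doses would rest on 3 subjects.

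**Precision.** The one-sided 95% upper limit for the DLT rate is 1 − 0.05^(1/3) = 63% after 0/3 and 1 − 0.05^(1/6) = 39% after 0/6. The six-subject rule also accepts 1/6, where the limit is about 58%.

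**Whole design.** On the same four curves, applying 10.2 whenever a dose proved too toxic, 62 to 74% of declared MTDs rested on 3 subjects, against none when 6 were required. The mean true DLT rate at the MTD fell only from 18.6–22.0% to 18.1–20.8%.

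**The case against.** The strongest reply is that 10.2 is a one-line summary and the operative text lies elsewhere. That largely stands. Four stronger readings that a reader might infer are not supported.

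- **That the plan accepts an MTD on 3 subjects.** Protocol 4.6 sets the criterion at fewer than 2 of 6, and Protocol 4.3.1.2 and SAP 4 require the back-fill. Taken as a whole, the plan does not accept it; only the 10.2 sentence does.
- **That 10.2 governs Cohorts 21–25 by default.** The synopsis and Protocol 4.3.2 carry the same 3+3 design and MTD definition to IS3w,1w, and the combination definition in 4.6 has no schedule limit. The SAP introduction lists protocol versions only to Amendment 11, so the silence of SAP 4 on IS3w,1w looks like version lag.
- **That 2 DLTs among the first 3 subjects has no rule.** 10.2 is silent, but Protocol 4.3.1.2 and SAP 4 both cover more than 1 of 3.
- **That a wrong MTD sets the expansion dose.** Combination expansion opens at the mBED, which has its own limit of 1 DLT in 6 plus response and trough criteria (Protocol 4.3.2). Expansion also has toxicity boundaries (Protocol 4.5).

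It is also fair that the effect is modest at the target DLT rate, and that precision stays poor at 1/6 even with 6 subjects. The escalation figures are not available in the text reviewed and may show the back-fill. The optional fourth subject (Protocol 4.1) could make the lower cohort 4 rather than 3.

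What remains is that 10.2 prescribes a different action from three other places on the same trigger, and that 4.3.2 writes out no step to settle it for the open cohorts.

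**Conclusion.** The contradiction is real and should be removed, but it is one of drafting rather than design. Followed literally, 10.2 drops a check that would overturn about 10% to 16% of doses passed on 0/3 at true DLT rates of 20% to 25%, and about 22%, 35% and 50% at 30%, 40% and 50%. Over all passing routes, requiring 6 subjects lowers acceptance from 60.0% to 53.4% at a true rate of 25%, and from 30.9% to 23.3% at 40%. The average DLT rate at the declared MTD changes little; the larger change is in how many MTDs rest on 3 subjects.

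These figures assume independent DLTs, a constant rate at each dose and cohorts of exactly 3 or 6 evaluable subjects. The DLT rates and simulated curves are assumptions, since the documents give none. The consequence is limited because the MTD acts as a ceiling and the mBED is the dose taken into expansion.

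**What to change.** Reconcile Protocol 10.2 with Protocol 4.6, Protocol 4.3.1.2 and SAP 4. Replace the 10.2 sentence with a reference to the 4.6 definition, so that the next lower dose is the MTD only once fewer than 2 of 6 evaluable subjects there have had a DLT. State in Protocol 4.3.2 and in SAP 4 that the same rule, including the fill to 6, covers both IS2w,2w and IS3w,1w. A reference to 4.6 also deals with a lower dose that fails at 6, since that dose then does not meet the definition.

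The cost is one replaced sentence in 10.2 and one added sentence each in Protocol 4.3.2 and SAP 4; the SAP edit can be made when the SAP is updated to Amendment 12. No subjects are needed beyond the up to 3 back-fill subjects that the 4.6 definition already implies, and no analysis changes.

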10.3. Analysis Methods

Subjects completing the first cycle of treatment with at least 75% of study drug compliance or experiencing a DLT during the first cycle (28 days) of treatment, will be considered evaluable for the occurrence of DLTs. The 3 + 3 design targets a DLT rate for the MTD of approximately 20–25%.

Summary statistics for continuous variables will include the mean, standard deviation, median and range (minimum/maximum). Categorical variables will be presented as frequency counts and percentages.

See [Section 10.6](#) for efficacy analysis methods.

10.3.1. Handling of Missing Data

For summary statistics, missing data will not be imputed; results will be reported based upon observed data.

10.3.2. Analysis Populations

The Safety population is defined as subjects who receive at least one dose of study drug(s).

The DLT evaluable population includes subjects in dose escalation cohorts who complete the first cycle of treatment with at least 75% of study drug compliance or experience a DLT during the first cycle (28 days) of treatment.

The Efficacy evaluable population is defined as subjects who complete the first scheduled post-baseline efficacy evaluation (scheduled on C3D1 for B-cell lymphoma subjects and C2D1 for AML subjects) or develop progression of disease or death prior to the first scheduled post-baseline efficacy.

The PK population will include all subjects who receive at least 1 dose of voruciclib or venetoclax and have at least 1 non-missing post-dose concentration value.

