Tumor lysis syndrome (TLS) includes electrolyte abnormalities (hyperkalemia, hypocalcemia, hyperuricemia, and hyperphosphatemia), cardiac dysrhythmias, and renal failure. Guidance on categorizing AML and CLL subjects for risk of TLS ([Appendix 9](#)), as well as a monitoring plan based on the [Venclexta \[US Prescribing Information\] Rev 2022](#), is provided in [Table 24](#).

Differentiation syndrome (DS) was considered a contributing factor in the pneumonitis cases and was reported as a DLT in 2 subjects with AML enrolled in Cohort 2. Therefore, tumor cytorreduction with hydroxyurea should be considered in subjects with AML and high peripheral counts, and corticosteroids administered per institutional standards if DS is suspected.

STATISTICAL ANALYSIS

Subjects completing the first cycle of treatment or experiencing a DLT during the first cycle (28 days) of treatment, will be considered evaluable for the occurrence of DLTs. The 3 + 3 design targets a DLT rate for the MTD of approximately 20 to 25%.

Summary statistics for continuous variables will include the mean, standard deviation, median, and range (minimum/maximum). Categorical variables will be presented as frequency counts and percentages.

Response to treatment will be tabulated with 95% exact binominal confidence intervals (CIs), analyzing all subjects who complete the first scheduled post-baseline efficacy evaluation (scheduled on C3D1 for B-cell lymphoma subjects and C2D1 for AML subjects) or who experienced disease progression prior to completing the first scheduled post baseline disease assessment. The Kaplan-Meier method will be used to estimate PFS within subjects of the same tumor type. For PFS, subjects without documented progression will be censored at the date of last disease assessment.

Associations between PK findings, efficacy findings, and biomarker results will be explored by tests of association for binary endpoints (e.g., Fisher's exact test) and by T-tests (or appropriate non-parametric alternatives) for continuous variables.

TABLE OF CONTENTS

CLINICAL STUDY PROTOCOL	1
SPONSOR’S PROTOCOL SIGNATURE PAGE.....	2
INVESTIGATOR’S SIGNATURE PAGE.....	3
PROTOCOL SYNOPSIS	4
ABBREVIATIONS	21
1. BACKGROUND AND RATIONALE.....	24
2. STUDY OBJECTIVES	27
2.1. Primary Objectives	27
2.2. Secondary Objectives	27
2.3. Exploratory Objectives	27
3. SUBJECT ELIGIBILITY	28
3.1. Inclusion Criteria	28
3.2. Exclusion Criteria	29
4. STUDY DESIGN	31
4.1. Overall Study Design.....	31

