A Phase 2 study of venetoclax monotherapy in 32 patients with AML (30 with relapsed and/or refractory; 2 newly diagnosed), demonstrated a 19% response rate (2 CR and 4 complete remissions with incomplete hematologic recovery [CRi]) with a median duration of response (DOR) of 48 days. Venetoclax was generally tolerated up to doses of 1200 mg daily (Konopleva 2016). In another study, venetoclax in combination with azacitidine or decitabine in 57 previously untreated elderly AML patients was administered at doses up to 1200 mg. No dose-limiting toxicities (DLTs) were observed, but subjects at the 1200 mg dose had frequent dose reductions due to gastrointestinal (GI) events. Overall, a 61% remission rate was obtained with 14/57 CR and 21/57 CRi (DiNardo 2018).

These data demonstrate that targeted therapy specific for the apoptotic pathway can have significant clinical benefit for patients with both B-cell malignancies and AML. However, despite high response rates, patients are not cured by currently approved therapy and will generally experience disease progression, indicating the need for development of new agents with a complementary mechanism of action that either alone or in combination with venetoclax or other agents enhance disease clearance and circumvent disease resistance.

Myeloid cell leukemia protein 1 (Mcl-1) is a member of the Bcl-2 anti-apoptotic, pro-survival family of molecules that are commonly over-expressed in B-cell malignancies and AML. Overexpression of Mcl-1 is associated with poor prognosis and resistance to therapy. Mcl-1 is not inhibited by venetoclax, which is specific for Bcl-2, and increased expression of Mcl-1 can be a mechanism of resistance for venetoclax therapy. Acquired resistance of lymphoma cell lines to Bcl-2 inhibition in vitro has been shown to involve transcriptional upregulation of Mcl-1 (Yecies 2010). Additionally, non-clinical studies have also demonstrated the ability of Mcl-1 to render AML cells resistant to Bcl-2 targeted agents, and have demonstrated synergy in AML models between agents targeting Bcl-2 with those targeting Mcl-1 expression including cyclin-dependent kinase 9 (CDK9) inhibitors (Pan 2015, Bogenberger 2017, Luedtke 2017).

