10.6. Efficacy Analyses

For the Efficacy population, response to treatment will be tabulated with 95% exact binominal CIs.

The Kaplan-Meier method will be used to estimate PFS and DOR within subjects of the same tumor type. For PFS, subjects without documented progression will be censored at the date of last disease assessment.

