### **6.3 Efficacy Evaluable Set**

The Efficacy Evaluable Set is defined as subjects who complete the first scheduled post-baseline efficacy evaluation (scheduled on C3D1 for B-cell lymphoma subjects and C2D1 for AML subjects) or develop progression of disease or death prior to the first scheduled post-baseline efficacy. The Efficacy Evaluable Set will be utilized for the analyses of efficacy.

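### ORR is analysed only on a set that omits treated subjects who stop early, alive and without progression, so it can be inflated; the ORR ≥30% mBED criterion names no denominator.

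*Protocol*

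**What the plan says.** **The set.** Protocol 10.3.2 gives the main condition as "The Efficacy evaluable population is defined as subjects who complete the first scheduled post-baseline efficacy evaluation", scheduled at C2D1 in AML and C3D1 in B-cell disease. It then adds subjects who "or develop progression of disease or death prior to the first scheduled post-baseline efficacy" evaluation. SAP 6.3 repeats both conditions.

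**The synopsis.** Its Statistical Analysis section keeps subjects who complete that evaluation "or who experienced disease progression prior to completing the first scheduled post baseline disease assessment". Death is not mentioned.

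**Where it is used.** Protocol 10.6: "For the Efficacy population, response to treatment will be tabulated with 95% exact binominal CIs". SAP 6.3: "The Efficacy Evaluable Set will be utilized for the analyses of efficacy". SAP 8.6.2 applies it to ORR. Protocol 10.3.1 and SAP 7.4 do not impute missing values. Neither document plans an ORR in all treated subjects.

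**The decision rule.** Protocol 4.3.2, the synopsis and SAP 3.1.1 require ORR ≥30% for the combination mBED, "as compared to historical ORR of 19% with 400-800 mg venetoclax alone in relapsed/refractory AML", together with no more than 1 DLT in 6 and a trough concentration target. No denominator is named for the ORR. Protocol 1 describes the benchmark study as having 32 AML patients and says that it "demonstrated a 19% response rate (2 CR and 4 complete remissions with incomplete hematologic recovery".

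**The concern.** A subject who takes study drug, stops in Cycle 1 for an adverse event or by choice, and is alive without documented progression meets neither condition of the set. With no imputation and no all-treated analysis, nothing brings that subject back. If such subjects are non-responders, as most would be, leaving them out raises ORR.

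This matters because ORR also feeds a dose decision. The SRC is given a numerical cut-off without being told which subjects to divide by. If it uses the only set on which the plan defines an ORR analysis, it may compare an evaluable-only rate with a benchmark described on all 32 patients. Cohorts are small, so one subject more or less in the denominator can decide which side of 30% a dose falls on.

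The synopsis adds a second problem. A subject who dies before the first assessment without documented progression is out of the denominator under the synopsis and in it under Protocol 10.3.2 and SAP 6.3.

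**Working it through.** **1. Benchmark (Protocol 1).** (2 CR + 4 CRi)/32 = 6/32 = 18.75%, which rounds to the stated 19%. The denominator is all 32 patients described.

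**2. General relation.** Let d be the share of treated subjects outside the set, all taken as non-responders. Then all-treated ORR = evaluable ORR × (1 − d). The documents do not give d, so 0 to 20% is an assumption.

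| d | All-treated ORR when evaluable ORR is 30% |
|---|---|
| 0 | 30% |
| 5% | 28.5% |
| 10% | 27% |
| 20% | 24% |

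**3. Escalation sizes.** Protocol 4.1 allows a fourth subject, and Protocol 4.12 replaces those who leave Cycle 1 without a DLT. A level that loses one such subject therefore has 4 treated for 3 DLT-evaluable, or 7 for 6.

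| Treated | Responders | All treated | One excluded |
|---|---|---|---|
| 4 | 1 | 1/4 = 25% (below 30%) | 1/3 = 33% (meets it) |
| 7 | 2 | 2/7 = 28.6% (below) | 2/6 = 33% (meets it) |
| 3 | 1 | 1/3 = 33% (meets it) | 1/2 = 50% (meets it) |
| 6 | 2 | 2/6 = 33% (meets it) | 2/5 = 40% (meets it) |
| 6 | 1 | 1/6 = 16.7% (below) | 1/5 = 20% (below) |

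One exclusion flips the result at 4 or 7 treated, but not at 3 or 6.

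**4. Chance of showing ≥30% when the true all-treated ORR is 19%.** With N treated, the number excluded is M ~ Binomial(N, d). Given M, responders are X ~ Binomial(N − M, 0.19/(1 − d)). On the evaluable set the criterion is met if X/(N − M) ≥ 0.30; on all treated, if X/N ≥ 0.30, which is the d = 0 column.

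| N treated | d = 0 (same as all treated) | d = 10% | d = 20% |
|---|---|---|---|
| 3 | 0.469 | 0.469 | 0.469 |
| 4 | 0.166 | 0.298 | 0.397 |
| 6 | 0.320 | 0.326 | 0.360 |
| 7 | 0.131 | 0.260 | 0.345 |
| 12 | 0.180 | 0.249 | 0.342 |
| 18 | 0.110 | 0.181 | 0.285 |

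Hand check for N = 3: one responder is enough whatever the denominator, so the chance is 1 − 0.81³ = 0.469 at every d. For N = 4 on all treated, two responders are needed: 1 − 0.81⁴ − 4 × 0.19 × 0.81³ = 1 − 0.430 − 0.404 = 0.166.

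**5. Early death.** Synopsis: completed assessment, or progression. Protocol 10.3.2 and SAP 6.3: completed assessment, progression, or death. The conflict needs no assumption.

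**The case against.** Several objections carry weight.

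- **The mBED rule is not tied to this set.** It names no denominator, and SAP 7.7 and 8.6.2.1 report ORR by tumor type, regimen and overall, not by dose cohort. A reader might infer that the plan fixes the evaluable set as the basis for the dose decision. The documents do not say so. What stands is that the denominator is unstated.
- **The drop-out allowances are not d.** A reader might take the 10% in Protocol 10.1 or the 20% in SAP 4 as the share excluded. Those allowances cover failure to complete Cycle 1 for any reason except voruciclib-related AEs. They can therefore include early progressions and deaths, which stay in the set, and they omit the toxicity stops at issue.
- **A less tolerable dose is not necessarily flattered most.** The same rule caps DLTs at 1 in 6, and under Protocol 4.4 many Cycle 1 discontinuations for an AE are themselves DLTs. Two such leavers among 6 already fail the dose, and one changes nothing on the ORR side (step 3). Withdrawals and non-DLT stops can still shift the ratio.
- **An early stopper could still respond.** Protocol 4.13 and 4.17 separate stopping drug from leaving the study, and Appendix 3 schedules a marrow at EOS. CRi and MLFS do not need full count recovery. The documents do not say whether that marrow makes a subject evaluable. If it does not, a responder could be excluded and ORR could fall.
- **The benchmark source is not available here.** The protocol gives 32 patients but does not say whether that is every treated patient or an analysed subset.
- **There are mitigations.** SAP 7.9 calls the study exploratory, exact confidence intervals accompany ORR, and SAP 8.1 tabulates the size of each population, so exclusions would be visible.

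These points limit the size of the concern and how firmly it can be stated. They do not supply an all-treated ORR or a denominator for the rule, and they leave the synopsis conflict in place.

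**Conclusion.** The concern holds as a conditional one. The planned ORR can exceed the all-treated ORR because treated subjects who stop early, alive and without progression, are left out. If nobody is excluded there is no bias. A reader might conclude that ORR is inflated by a known amount; the documents give no excluded share, so they do not support that.

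The effect depends strongly on size. One exclusion can flip the result at 4 or 7 treated, while at exactly 3 or 6 treated the effect is nil or small. The rise from 0.18 to 0.34 at 12 treated is an illustration. It assumes a true all-treated ORR of 19%, an excluded share of 0 to 20%, and that every excluded subject is a non-responder. Since the mBED is identified before the 12-subject expansion opens, the rule is mostly applied at about 3 to 7 subjects.

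Two points need none of these assumptions: the ORR ≥30% criterion has no stated denominator, and the synopsis disagrees with Protocol 10.3.2 and SAP 6.3 on early death. The plan should be corrected on these points, though the defect does not undermine the study.

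**What to change.** 1. In Protocol 4.3.2, the synopsis and SAP 3.1.1, state that the ORR for the mBED criterion uses all treated subjects at the dose level.
2. In Protocol 10.6 and SAP 6.3 and 8.6.2, base the reported secondary ORR on the existing Safety set.
3. In both, count any assessed response, including one at the EOS marrow, and count subjects with no post-baseline assessment as non-responders.
4. Keep the Efficacy Evaluable Set ORR as a supportive analysis.
5. Add death before the first assessment to the synopsis definition so that it matches Protocol 10.3.2 and SAP 6.3.

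The cost is wording in the protocol and SAP, with no new data or visits. The downside is a slightly less favourable ORR whenever a treated subject leaves unassessed.
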